#### 4.2.8 Withdrawals, Dropouts, Lost to Follow-up

Subjects are free to withdraw from participation in the study for any reason at any time. The reason for terminating study participation will be recorded in each subject's medical records (source documents) and entered into the End of Study electronic Case Report Form (eCRF).

If a subject withdraws from the study, every effort was to be made to complete the end of treatment (EOT) assessments; however, if a subject withdraws consent, no further assessments should be performed and no additional data should be collected. Radius may retain and continue to use any data collected before consent was withdrawn.

#### 4.2.9 Missing, Unused, and Spurious Data

Unless otherwise specified, missing dates for onset of AEs and start dates of concomitant medications will be handled according to the Missing Date Imputation Method in Appendix 7.1.

#### 4.2.10 Visit Windows

CRF visits will be used for analysis. For the safety analysis, in the case of multiple observations at a specific visit, the observation which is the latest will be used. If more than one observation is made on the same day, an average value if continuous or the worst value if categorical will be included in the analysis.

### 4.3 Interim Analyses

At about 70% enrollment, an interim futility analysis will be provided to the IDMC. At that time, the total number of PFS events is expected to be around 119 (35% of the total events). At this interim data

Sponsor:	Radius		
Protocol:	RAD1901-308		
Document Version No.:	1.1 (Final)	Document Date:	10-MAY-2021

look, the IDMC will evaluate the primary endpoint in conjunction with other efficacy endpoints, including OS, ORR, DoR and CBR. These additional efficacy data will assist the IDMC to check consistency for the totality of the data. The IDMC will make 1 of the following recommendations according to the conditional power of the primary efficacy endpoint for all subjects (ESR1-mut and ESR1-mut-nd), which will be derived based on the observed data at the interim futility analysis.

- x } v ] v ] o v u } ] ( ] ] ( Z 2.5% } v ] ] } v o
- x Terminate enrollment of ESR1-mut-nd subjects due to futility if the conditional power is <20% at the alpha level of 2.5%
- x Other (specified in IDMC charter)

If the conditional power is < 20% for all subjects at the alpha level of 2.5%, further enrollment of ESR1-mut subjects will be evaluated by the IDMC. Study drug administration for ongoing subjects will remain unchanged unless otherwise determined by the Investigator.

The graphical display using predicted interval plots (PIPS) may be used to support the finding from the conditional power.

Details of statistical methods for the interim futility analysis are provided in the interim SAP Version 1.0 dated 17 August 2020.

#### 4.4 Subject Disposition

Subject disposition will be tabulated by treatment group (elacestrant vs SOC) and by SOC type (fulvestrant vs AIs) to include the number screened, the number randomized, the number treated, the number in each subject population for data analysis, the number remaining on treatment, the number who discontinued study drug and the primary treatment termination reason as recorded in the eCRF, and the number who discontinued the study as well as the primary reason for study withdrawal as recorded in the eCRF.

A by-subject data listing of study drug information including the primary reason for treatment discontinuation and study withdrawal as recorded in the eCRF, if applicable, will be presented.

#### 4.6 Medical History, Disease History and Prior Therapies

Medical history will be presented by MedDRA (version 23.0) system organ class and preferred term (PT), summarizing by treatment group (elacestrant vs SOC) and SOC type (fulvestrant vs AIs) using ITT population for ESR1-mut subjects and all subjects (ESR1-mut and ESR1-mut-nd).

The following summaries will be provided by treatment group and SOC type for the ITT, RE, CBE and PP populations for ESR1-mut subjects and all subjects (ESR1-mut and ESR1-mut-nd):

Summary of breast cancer history and baseline disease characteristics will include years since diagnosis, stage at initial diagnosis, TNM staging at initial diagnosis, stage at baseline, TNM staging at baseline, sites of disease and number of metastatic sites (0, 1, 2, H3). Sites of disease will be categorized as breast, bone, bone only, visceral (any, and brain, liver, lung) and other.

Data on breast cancer diagnosis, hormone receptor status and HER2 status are based on local historical results. Summary of breast cancer histopathology will include source of tissue (original diagnosis, most recent biopsy, or interim time point), histology and grade, results for ER status including immunohistochemistry (IHC) percentage, results for progesterone receptor status including IHC percentage, results for HER2 status including IHC result and in situ hybridization (ISH) HER2/CEP17 ratio, if performed. Local historical data, including tissue source and results, for ESR1 and PIK3CA mutations will be summarized.

Summary of prior systemic anticancer therapies will include:

- x Number of subjects with neoadjuvant therapy
- x Number of subjects with adjuvant therapy
- x Number of subjects with neoadjuvant and/or adjuvant (neo/adjuvant) endocrine therapy, and each type of endocrine therapy in neo/adjuvant setting
- x Number of subjects with neo/adjuvant chemotherapy

Sponsor:	Radius		
Protocol:	RAD1901-308		
Document Version No.:	1.1 (Final)	Document Date:	10-MAY-2021

- x Number of subjects with neo/adjuvant targeted therapy
- x Total duration of AI therapy in any setting
- x In advanced/metastatic setting
  - o Number of lines of endocrine therapy (1 or 2) with documented progression
  - o Best response to last line of endocrine therapy
  - o Number of lines of chemotherapy (0 or 1)
  - o Number of lines of targeted therapy
  - o Number of subjects with each type of endocrine therapy

#### 4.7 Efficacy Evaluation

PFS and OS will be analyzed based on ITT population. ORR and CBR will be analyzed using RE population, and CBE population, respectively.

Final analysis of primary endpoints will be performed when approximately 160 events of objective disease progression or death based on IRC assessment have occurred among the ESR1-mut subjects and 340 events have occurred among all subjects (ESR1-mut and ESR1-mut-nd).

Analysis of primary and secondary efficacy endpoints will adjust for the randomization stratification factors (obtained from eCRF). For the analyses of all subjects, these stratification factors include ESR1-mutational status (ESR1-mut vs ESR1-mut-nd), prior treatment with fulvestrant (yes vs no), and presence of visceral metastases (yes vs no). For the analyses of ESR1-mut subjects, the stratification factors include prior treatment with fulvestrant (yes vs no) and presence of visceral metastases (yes vs no).

##### 4.7.1 Primary Efficacy Endpoints

##### 4.7.1.1 Primary Analysis

The primary efficacy endpoints of this study are

- x IRC-assessed PFS in the ESR1-mut subjects
- x IRC-assessed PFS in all subjects (ESR1-mut and ESR1-mut-nd)

which will be analyzed using the ITT population for the ESR1-mut subjects, and all subjects (ESR1-mut and ESR1-mut-nd), respectively.

PFS is defined as the duration (in months) from the date of randomization to the earliest date of documented disease progression (RECIST v1.1) as assessed by the blinded IRC, or death due to any cause regardless of whether the subject withdraws from randomized therapy (i.e., date of PFS event or censoring – date of randomization + 1). Subjects who receive any new systemic anticancer therapy before disease progression will be censored at the date of the last adequate tumor assessment before initiation of new systemic anticancer therapy.

Tumor assessment visits are scheduled every 8 weeks  $\pm$  7 days. Subjects without documented progression or death will be censored at the date of last adequate tumor assessment. Subjects without any post-baseline tumor assessments will be censored at the date of randomization (i.e., Day 1); however, if the subject dies within 2 visits of baseline without any post-baseline tumor assessments, this will be counted as an event. If the subject progresses or dies immediately after 2 or more consecutive missed visits, the subject will be censored at the time of the latest evaluable RECIST 1.1 assessment prior to the 2 missed visits (Note: a visit with a response of NE is not considered as missed visit). Given the scheduled visit assessment scheme (i.e., every 8 weeks  $\pm$  7 days), 2 missing visits will equate to 18 weeks since the previous RECIST assessment, allowing for early and late visits (i.e., 2 x 8

Sponsor:	Radius		
Protocol:	RAD1901-308		
Document Version No.:	1.1 (Final)	Document Date:	10-MAY-2021

weeks + 1 week for an early assessment + 1 week for a late assessment = 18 weeks). Detailed censoring rules are described in Table 2.

The hazard ratio (HR) and 95% CI for the treatment effect will be estimated using the stratified Cox proportional hazards regression model with Efron method of handling ties, stratified by randomization stratification factors (as described in section 4.7). Confidence interval will be constructed using the profile likelihood method.

The Kaplan–Meier curve of PFS of the 2 treatment groups will be displayed graphically, along with median event times and 95% CIs, for 2 sets of study subjects, ESR1-mut subjects and all subjects.

#### 4.7.1.2 Assumptions of Proportionality

The assumption of proportional hazards will be tested first by examining Kaplan–Meier curves and plots of the log of negative log of estimated survival probability versus log (time) and, if these raise concerns, by fitting a time dependent covariate (adding a treatment-by-time or treatment-by-ln(time) interaction term) to assess the extent to which this represents random variation.

If a lack of proportionality is evident, the HR from the primary analysis can still be meaningfully interpreted as an average HR over time unless there is extensive intersection of the survival curves.

In addition, the Restricted Mean Survival Time (RMST) method ([Royston and Parmar 2013](#)) permits inference over a specified time period, with an area-under-the-curve type approach, in situations with non-proportional hazards. Details for RMST are described in the section of sensitivity and supplemental analysis below.

#### 4.7.1.3 Sensitivity Analyses

The following sensitivity analyses will be performed.

**Sensitivity Analysis 1** (Actual event PFS analysis): In this analysis, PFS events recorded after missing 2 or more consecutive tumor assessments will be included as events, with the PFS event date defined as the actual event date after the 2 missed tumor assessments.

**Sensitivity Analysis 2** (Backdating PFS analysis): In this analysis, PFS events recorded after missing 2 or more consecutive tumor assessments will be included as events, with the PFS event date defined as the date of the next scheduled tumor assessment after the last adequate tumor assessment.

For example, suppose a subject had the last adequate tumor assessment in January, missed tumor assessments in March and May, and then had a PFS event in July. In Sensitivity Analysis 1, the subject will have the actual PFS event date in July as the event date; in Sensitivity Analysis 2, this subject will have the next scheduled tumor assessment date (after the last adequate tumor assessment in January) in March as the event date.

The above 2 sensitivity analyses will be performed in the same manner as the primary efficacy analyses.

Sponsor:	Radius		
Protocol:	RAD1901-308		
Document Version No.:	1.1 (Final)	Document Date:	10-MAY-2021

**Sensitivity Analysis 3** (Unstratified analysis): As a sensitivity analysis to assess the impact of stratification (obtained from eCRF), the 2 treatment groups will be compared using the unstratified log-rank test. The HR together with the associated 95% confidence interval obtained using the unstratified Cox regression model will also be presented.

**Sensitivity Analysis 4** (COVID-19 analysis): To assess potential COVID-19 impact, if subjects died due to COVID-19 infection without PD, PFS date will be censored at the death date. Analysis of PFS will be performed in the same manner as the primary efficacy analyses if at least 5% of deaths are due to COVID-19 infection.

**Sensitivity Analysis 5** (Per-Protocol Population analysis): This analysis will be performed based on PP population in the same manner as the primary efficacy analyses if the primary endpoints are statistically significant.

#### 4.7.1.4 Restricted Mean Survival Time Analysis

The RMST methodology is independent of the proportional hazards assumption and can be used as a supplemental analysis to explore the robustness of the primary analysis results. The restricted mean

should not exceed the minimum of the largest follow-up time for both treatment groups so that the RMST of both treatment groups being evaluated can be adequately estimated and comparison

follow-up so that the majority of survival outcomes will be covered by the time interval. The RMST up

The RMST analysis of the primary efficacy endpoints will be performed with the randomization stratification factors (as described in section 4.7) as covariates.

RMST estimate of the IRC-assessed PFS with the 95% CI will be provided for each treatment group. The treatment effect will be assessed based on the difference of RMST in IRC-assessed PFS between the treatment groups. The associated 95% CI for the difference in means and a p-value will be generated.

#### 4.7.2 Key Secondary Efficacy Endpoints

##### 4.7.2.1 Key Secondary Analysis

Key secondary efficacy endpoints include the following:

- x OS in ESR1-mut subjects
- x OS in all subjects (ESR1-mut and ESR1- mut-nd)

Overall survival is defined as the time from the date of randomization until death due to any cause regardless of whether the subject withdraws from randomized treatment or receives another anticancer therapy (i.e., date of death or censoring – date of randomization + 1). Any subject not known

Sponsor:	Radius		
Protocol:	RAD1901-308		
Document Version No.:	1.1 (Final)	Document Date:	10-MAY-2021

to have died at the time of analysis will be censored based on the last recorded date on which the subject was known to be alive. The last known alive date is the date subject last confirmed to be alive from eCRF Survival Status page.

Analyses of OS in ESR1-mut subjects and in all subjects (ESR1-nut and ESR1- mut-nd) will be performed using the ITT population.

For each of the 2 sets of study subjects, OS will be analyzed at the following 2 time points

- x At the time of the primary PFS analysis (when approximately 160 and 340 PFS events are observed among the ESR1-mut and all subjects (ESR1-mut and ESR1- mut-nd), respectively, and
- x At the time of the final OS analysis (when approximately 50% of the subjects have died)

At each time point, analyses of OS will be conducted in a similar manner as the primary analysis of PFS. Number and percentage of subjects with event and subjects censored will be tabulated by treatment group.

Kaplan-Meier method will be used to estimate the survival distribution function of OS. The following summaries by treatment group will be provided: median OS and 95% CI, 1st and 3rd quartiles and 95% CI, overall survival rates and 95% CI at months 6, 12, and 18 (and every 6 months thereafter until the end of follow-up or no more subjects are at risk).

The difference in the key secondary endpoints between the 2 treatment groups will be analyzed using the stratified log-rank test, with the randomization stratification factors (as described in section [4.7](#)) for generation of the p-value.

The HR and 95% CI for the treatment effect will be estimated using the stratified Cox proportional hazards regression model with Efron method of handling ties, stratified by randomization stratification factors (as described in section [4.7](#)). Confidence interval will be constructed using the profile likelihood method.

The Kaplan–Meier curve of OS of the 2 treatment groups will be displayed graphically, along with median event times and 95% CIs, for 2 sets of study subjects, ESR1-mut subjects and all subjects (ESR1-mut and ESR1-mut-nd).

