4. INVESTIGATIONAL PLAN

4.1. Overall Study Design

This is an international, multicenter, randomized, open-label, active-controlled, event-driven, Phase 3 clinical study comparing the efficacy and safety of elacestrant to the SOC options of either fulvestrant or an AI in post-menopausal women and men with ER+/HER2- mBC whose disease has relapsed or progressed on at least 1 and no more than 2 prior lines of endocrine therapy for mBC, which must have included CDK4/6i therapy in combination with fulvestrant or an AI. Subjects must have received no more than 1 line of cytotoxic chemotherapy in mBC. Endocrine monotherapy with 1 of the SOC drugs (fulvestrant, anastrozole, letrozole, exemestane) must be an appropriate treatment option for subjects enrolled in this study. The primary endpoints of IRC-assessed PFS will be analyzed in ESR1-mut subjects and in all subjects (ESR1-mut and ESR1-mut-nd) using the Hochberg procedure to adjust for the multiplicity of the primary endpoints. A schematic of the study design is provided in [Figure 4](#).

Subjects who meet all eligibility criteria will be enrolled into the active treatment phase of the study. During this phase of the study, subjects will receive study drug as defined in the protocol and will undergo the protocol-defined safety, efficacy, and exploratory assessments. Subjects will continue to receive treatment until the following: disease progression, a clinically significant AE, significant study noncompliance, the subject is unable to receive study treatment for > 14 consecutive days, treatment discontinuation in the best interest of the subject, or subject refuses treatment as defined in [Section 5.3.1](#) requires subject withdrawal.

Subjects who discontinue the active treatment phase due to disease progression will enter a follow-up phase during which survival data and the start date and regimen name of the first new anti-cancer therapy will be collected. For subjects who discontinue treatment for reasons other than disease progression, death, consent withdrawal, toxicity, or loss to follow-up and who do not begin new anti-cancer therapy, tumor assessments will continue until disease progression or the first new anti-cancer therapy is initiated. At that time, subjects will discontinue tumor assessments and continue to be monitored for survival data and the initiation of the first new anti-cancer therapy.

[figure not shown]

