4.4. Disease Progression and Tumor Assessments

Tumor assessments will be performed every 8 weeks (\pm 7 days) from the date of randomization during the active treatment phase of the study. Subjects with bone lesions identified by radionuclide bone scan or whole body magnetic resonance imaging (MRI) at baseline (during Screening) will have repeat bone scans or whole body MRI (using the same modality as used

during Screening) performed every 24 weeks (± 7 days) from the date of randomization and at time of confirmation of a CR. All assessments will be performed as scheduled at the required intervals according to the Schedule of Events ([Appendix 2](#)), regardless of any dosing delay to prevent the introduction of bias into the assessment of efficacy.

Tumor assessments will be performed until radiographically- and/or clinically-documented (ie, for photographed or palpable lesions) disease progression as per RECIST v1.1, initiation of new anti-cancer therapy, or discontinuation from overall study participation ([Section 7.4](#)), whichever occurs first.

Subjects who discontinue study treatment for reasons other than radiographically- and/or clinically- (ie, for photographed or palpable lesions) documented disease progression, per RECIST v1.1, will continue to have tumor assessments performed every 8 weeks (± 7 days) in the follow-up period, and bone scans or whole body MRI (as applicable) as clinically indicated and/or every 24 weeks (± 7 days) until RECIST-defined disease progression, initiation of the first new anti-cancer therapy, or discontinuation from overall study participation (eg, death, withdrawal of consent, lost to follow-up), whichever occurs first.

Subjects no longer undergoing tumor evaluations will continue to be monitored every 8 weeks for survival data and the initiation of the first new anti-cancer therapy.

The follow-up period will conclude at the time of the final OS analysis when approximately 50% of subjects in the study have died.

Efficacy analyses will be performed using tumor assessments made by the blinded IRC as the primary data source. Analyses of endpoints based on local Investigator assessment will also be performed as supportive analyses.

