8.5. Post-Treatment Follow-Up

Post-treatment Follow-Up is to occur every 8 weeks (± 7 days) (see [Appendix 2](#)).

For subjects who discontinue study treatment because of objective disease progression or clinical progression in the absence of progression by RECIST, survival data will be collected every 8 weeks (± 7 days), calculated from the last dose of study treatment, for the duration of the study. The start date and regimen name of the first new anti-cancer therapy will also be collected. Telephone contact is acceptable.

Note: Subjects who discontinue treatment for reasons other than disease progression and who do not begin a new anti-cancer therapy will continue to have tumor assessments every 8 weeks (± 7 days) from the date of randomization, and bone scans or whole body MRI every 24 weeks (± 7 days) as indicated, until disease progression is documented, or new anti-cancer therapy is initiated, at which time they will continue to be monitored every 8 weeks (± 7 days) for first new anti-cancer therapy and survival for the duration of the study.

At any time after 30 days from the last dose of study treatment, the Investigator may report any SAE that he/she believes is related to study treatment.

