8.6. Study Completion

The study will be complete when approximately 50% of subjects have died. However, subjects will be provided with study treatment, if still on active treatment, until all subjects discontinue

study participation or elacestrant is approved for marketing in a subject's country, at which time the study may be closed for subject participation.

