- f. For subjects who discontinue study treatment due to objective disease progression, survival data and start date and regimen name of the first new anti-cancer therapy should be collected every 8 weeks (± 7 days) calculated from the last dose of study drug for the duration of the study. For subjects who discontinue treatment for reasons other than disease progression, and who do not begin new anti-cancer therapy, tumor assessments will continue every 8 weeks (± 7 days, from the date of randomization), and for subjects with bone lesions at baseline radionuclide bone scan or whole body MRI will be performed every 24 weeks (± 7 days), as indicated, until disease progression is documented, or new anti-cancer therapy is initiated; at that time, they will continue to be monitored every 8 weeks for survival and first new anti-cancer therapy information for the duration of the study.
- g. Informed consent must be obtained prior to any protocol-required assessments (except for certain imaging assessments if they meet the criteria defined in [Table 20](#)).
- h. ER and HER2 status must be confirmed per local laboratory testing.
- i. Prior anti-cancer therapy, including drug names, treatment start/end date, dose, setting (neoadjuvant, adjuvant, or recurrent/metastatic line of therapy), best response, date of disease progression, and reason for treatment discontinuation, are to be recorded.

- j. Randomization is to occur after eligibility is determined by the study site and confirmed by the Medical Monitor. The planned first dose of C1D1 is to start within 1 day after randomization; randomization may occur on D-1 or on D1. Note: there is no Day 0 in this study. C1D1 is the date of first dose of study drug.
- k. PRO questionnaires are to be completed by the subject using the electronic tablet provided while in clinic (cannot be taken home) at the beginning of the study visit and prior to any other assessments or significant interactions with site staff. PRO questionnaires will be performed on C1D1, C1D15, C2D1, and D1 of each subsequent cycle through C4, then D1 of every other cycle thereafter starting with C6 (ie, C2, C3, C4, C6, C8, C10, etc), at EOT, and at the Safety Follow-Up visit (unless this visit is performed via phone contact). Note: If a certified translation for any PRO questionnaire is not available for a subject, that specific PRO assessment can be omitted, but the reason must be documented.

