		Cycle 1 c		Subsequent Cycles c		PTx Safety Follow-up 30 days after last dose of study drug e (± 3 d)	PTx Follow-up every 8 week f (± 7 d)
Study Day (visit window in days)	Day -35 to -1	Day 1 d	Day 15 d (± 2 d)	Day 1 d (±2 d)	(+14 d; within 14 d of last dose of study drug)		
Elacestrant group dd		{ ----- yOnce Daily					
SOC treatment group -aromatase inhibitor ee		{ ----- yOnce Daily					
SOC treatment group – fulvestrant ff		C1D1, C1D15, and Day 1 of every subsequent cycle					
Drug compliance gg		{----- y					
Adverse events hh		{----- y					

Sponsor:	Radius		
Protocol:	RAD1901-308		
Document Version No.:	1.1 (Final)	Document Date:	10-MAY-2021

Procedures/Assessments	Screening a	Active Treatment Period			End of Treatment (EOT) b	Post-Treatment (PTx)	
		Cycle 1 c		Subsequent Cycles c			
Study Day (visit window in days)	Day -35 to -1	Day 1 d	Day 15 d (± 2 d)	Day 1 d (±2 d)	(+14 d; within 14 d of last dose of study drug)	PTx Safety Follow-up 30 days after last dose of study drug e (± 3 d)	PTx Follow-up every 8 week f (± 7 d)
Prior/Concomitant medications/treatments ii	{----- y						
Survival follow-up for subjects who discontinue treatment f						X	

- a. All Screening assessments must be completed within 35 days prior to randomization (all imaging must be completed within 28 days prior to randomization unless otherwise specified). All surgical procedures related to breast cancer diagnosis must be recorded.
- b. If EOT falls on Day 1 of a cycle and the subject is withdrawing, the EOT assessments are to be completed instead of the Cycle Day 1 assessments. Assessments completed within the previous 14 days do not have to be repeated at the EOT visit.

Sponsor:	Radius		
Protocol:	RAD1901-308		
Document Version No.:	1.1 (Final)	Document Date:	10-MAY-2021

- 
- c. A Cycle is 28 days.
  - d. All assessments are to be performed pre-dose on scheduled visit days unless otherwise indicated. Procedures maybe performed  $\pm 2$  days relative to the visit.
  - e. Onsite visit preferred; if this is not feasible, telephone contact is acceptable. If follow-up assessments are conducted by telephone, the PROs are to be omitted.

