#### 4.7.2.2 Sensitivity Analyses

A sensitivity analysis for OS will examine the censoring patterns to rule out attrition bias with regard to the treatment comparisons, achieved by a Kaplan-Meier plot of time to censoring where the censoring indicator of OS is reversed.

The number of subjects prematurely censored will be summarized by treatment group. A subject would be defined as prematurely censored if their survival status was not defined at the data cut-off (DCO).

Sponsor:	Radius		
Protocol:	RAD1901-308		
Document Version No.:	1.1 (Final)	Document Date:	10-MAY-2021

In addition, duration of follow-up will be summarized using medians:

- x In all subjects: Time from randomization to the date of death (i.e. overall survival) or to the date of censoring (date last known to be alive) for censored subjects regardless of treatment group.
- x By treatment group: Time from randomization to the date of death (i.e. overall survival) or to the date of censoring (date last known to be alive) for censored subjects

To assess potential COVID-19 impact, if subjects died due to COVID-19 infection, OS date will be censored at the death date. Analysis of OS will be performed in the same manner as the primary key secondary analysis if at least 5% of deaths are due to COVID-19 infection.

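### The OS last-known-alive date comes from one eCRF page, survival contact is scheduled only after treatment or tumor follow-up ends, and no fallback date is given

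*SAP*

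**What the plan says.** SAP 4.7.2.1 censors subjects not known to have died at the last recorded date they were known alive. The next sentence defines that date: "The last known alive date is the date subject last confirmed to be alive from eCRF Survival Status page". No other source is named.

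Survival contact is scheduled as follows:

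- **Schedules.** SAP Table 1 and protocol Table 18 carry the row "Survival follow-up for subjects who discontinue treatment", marked only under post-treatment.
- **Protocol 4.1.** Subjects who stop treatment for progression "will enter a follow-up phase during which survival data and the start date" of the next therapy are collected.
- **Protocol 8.5.** After progression, the 8-weekly contacts are "calculated from the last dose of study treatment, for the duration of the study". Footnote f of Table 18 says the same: "calculated from the last dose of study drug for the duration of the study".
- **Protocol 4.4.** "Subjects no longer undergoing tumor evaluations will continue to be monitored every 8 weeks for survival data".

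Protocol 8.6 allows for subjects still being treated when the study completes: "subjects will be provided with study treatment, if still on active treatment".

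The imputation rules in SAP 4.2.9 and Appendix 8.1 cover adverse events, concomitant medications and post-treatment anti-cancer therapy. They do not cover a missing alive date.

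**The concern.** A living subject still on study drug has visits, doses, laboratory results and scans that prove survival, but SAP 4.7.2.1 does not use them. The one source it names is a page whose content, survival status, is scheduled for collection only later. Read literally, a programmer could find no date for such a subject and would have no rule to apply.

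This matters because the loss would be informative. A death on treatment enters the OS analysis as an event, whereas alive time on treatment would not enter the risk sets. If elacestrant prolongs PFS, more elacestrant than SOC subjects are on treatment at any cut-off, so more survival time is lost in that arm. OS is the key secondary endpoint, and its stated power is only 60% in all subjects and 39% in ESR1-mut subjects.

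**Working it through.** **1. The plan's own OS power.** Inputs are from SAP 4.2.6: 239 deaths with HR 0.75 (all subjects) and 114 deaths with HR 0.73 (ESR1-mut), 1-sided 2.5%, 1:1 allocation. Power = Φ(√d/2 × |ln HR| − 1.96).

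- All subjects: √239/2 × 0.2877 = 2.224; Φ(0.264) = 60.4% (stated 60%).
- ESR1-mut: √114/2 × 0.3147 = 1.680; Φ(−0.280) = 39.0% (stated 39%).

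The stated figures reproduce.

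**2. When the final OS analysis falls.** Inputs: median OS 25 months (SOC) and 25/0.75 = 33.3 months (elacestrant), 239 subjects per arm, and the 15-month enrollment period in protocol 11.3.5. Assumed: exponential survival and uniform accrual. With a cut-off at month 36.5, follow-up runs from 21.5 to 36.5 months. The expected proportions dead are 0.549 (SOC) and 0.451 (elacestrant), so deaths = 239 × (0.549 + 0.451) = 239.

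**3. How many are still on elacestrant then.** Protocol 5.3.1 expects about 4 months on treatment. If treatment time is exponential with median 4 months, the proportion still treated is (1/15) × (4/ln 2) × (2^(−21.5/4) − 2^(−36.5/4)) = 0.0086, or about 2 of 239 subjects. Protocol 5.3.1 also expects responders to stay longer, which raises the number.

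**4. Size if every living on-treatment subject lacks a date.** Simulations of all subjects at 239 deaths used the SAP's OS assumptions and PFS HR 0.667, and took such subjects out of the risk sets. The SOC median PFS for all subjects, the curve shape and the PFS–OS correlation are not in the documents and were assumed.

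| Assumption | OS HR estimated (true 0.75) |
|---|---|
| SOC median PFS 2.6–4.0 months, fitted to 340 PFS events at 96 deaths | 0.757–0.772 |
| SOC median PFS 5.3 months (the plan's ESR1-mut figure) | 0.776–0.811 |
| Half of the on-treatment subjects have a date, either PFS assumption | 0.753–0.778 |

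A further simulation, varying PFS and treatment duration, gave about 0–8 SOC and 1–18 elacestrant subjects alive on treatment and an estimate of about 0.75–0.79. I take this as the working range. Its top end is a shift of ln(0.79/0.75) = 0.052 on the log scale. With SE about 2/√239 = 0.129, that is 0.4 SE. The formula in step 1 then gives Φ(√239/2 × 0.2357 − 1.96) = Φ(−0.138), or about 45% power. At the bottom end power stays at 60%.

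**5. ESR1-mut subjects.** Here 5.3 months is the plan's own assumption. At 114 deaths, with about 1–4 SOC and 4–12 elacestrant subjects affected, a true HR of 0.73 is estimated at 0.756–0.799 if none has a date.

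**6. Wider gap.** Protocol 4.4 can be read as leaving out subjects who are off treatment but still in tumor follow-up. If every living progression-free subject lacks a date, the final all-subject estimate is 0.80 (exponential PFS, SOC median 5.3 months). It reaches 0.84–0.88 with a heavy-tailed PFS curve (Weibull shape 0.6), a shape the documents do not suggest.

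**7. PFS-time look.** More subjects are then on treatment. The estimate is 0.82–0.85 if 340 PFS events coincide with 96 deaths, 0.78–0.86 at month 27 and 0.77–0.84 at months 30–33. Under the wider gap it is 0.89–0.92. The timing is unclear because the SAP's OS medians give about 180–218 deaths at 30–33 months, not 96.

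**8. Direction check.** With equal PFS and no OS effect the estimate does not move (0.995 with all dates, 0.993 without). The shift comes from the PFS difference.

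**The case against.** The strongest reply is that the premise depends on material outside the documents. The schedules list contacts, not eCRF pages, and nothing confines the Survival Status page to post-treatment use. Several passages suggest that a date is expected for everyone:

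- The general censoring sentence in SAP 4.7.2.1 is broader than the one that follows it.
- SAP 4.7.2.2 treats an undefined status at the data cut-off as the exception, with no exemption for treated subjects.
- SAP 4.12.1 uses a last-known-alive date for fulvestrant exposure.
- Protocol 4.4 speaks of subjects continuing to be monitored, which may imply earlier tracking.
- The IDMC reviews OS while many subjects are still on treatment.

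Nor does the SAP say that a subject with a blank date leaves the risk set. That handling is an assumption of the simulations.

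All of this stands as a limit on the finding. A reader might infer that treated subjects will have no alive date and that the OS analysis is therefore biased. The documents do not support that, because they do not show how the page is completed. A reader might also infer a large loss of power. The larger figures need the ESR1-mut SOC median PFS applied to all subjects, or every progression-free subject to lack a date.

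What the reply does not do is close the gap. None of these passages requires the page at the cut-off, names another source or gives a rule for a blank date. The reverse Kaplan–Meier plot and the premature-censoring counts in SAP 4.7.2.2 could reveal the problem but would not correct it.

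**Conclusion.** The point holds as a conditional one. The SAP names a single source for the alive date, the scheduled survival contacts do not reach subjects still on treatment, and there is no fallback. Whether this causes bias depends on eCRF practice that the documents do not show.

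In the worst case for on-treatment subjects, the final all-subject OS hazard ratio moves from 0.75 to about 0.75–0.79. This rests on assumed PFS and treatment duration, proportional hazards and no dropout from OS. The PFS-time estimate could move more, but that look carries alpha 0.0001; the final analysis carries 0.0499 when both PFS endpoints are significant.

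A false superiority claim is not at issue. Under SAP 4.2.6, OS is tested only in a population where PFS is significant, and when elacestrant has the longer PFS the shift is against elacestrant. The cost would be a somewhat pessimistic OS estimate and some lost power. The change is worth making because it is nearly free.

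**What to change.** In SAP 4.7.2.1, define last known alive as the latest date, on or before the cut-off, from any record showing the subject alive: visit, dose, laboratory sample, ECG, tumor assessment, PRO, subsequent therapy or Survival Status page. Use the same date for the follow-up and premature-censoring summaries in 4.7.2.2 and for the fulvestrant exposure end date in 4.12.1. State whether the Survival Status page is completed for all living subjects at each cut-off.

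The cost is one SAP sentence and a derived-date program, with no new data collection. If the page is already completed for everyone, the change does no harm.
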